Trapezio – metacarpal arthroplasty:

comparison of ARPE[®] prosthesis with the literature

PROTOCOL NUMBER (Study ID): ORTHO.CR.E16

PROTOCOL VERSION: V1.0 dd 12 Nov 2012

GENERAL INFORMATION

Study Sponsor: BIOMET Global Supply Chain Center B.V. [name] The Netherlands

TITLE	Trapezio-metarcarpal arthroplasty: a comparison of ARPE prosthesis with the literature
SHORT TITLE	Arpe prospective study
DESIGN	Non-controlled, prospective cohort study in single centre
STUDY DURATION	2013- 2020
STUDY CENTRE	Single centre in Belgium
POPULATION	Inclusion of 100 subjects at single centre
PRIMARY Research objectives	The primary objective is to compare functional outcome at 3 years after trapezio-metarcarpal arthroplasty with trapeziectomy and trapeziectomy with ligament reconstruction and tendon interposition. Literature values obtained by a recently published meta analysis ¹ will be used.
SECONDARY Research Objectives	Secondary objectives are: - to compare functional outcome at 1 and at 5 years after trapezio-metarcarpal arthroplasty with trapeziectomy and trapeziectomy with ligament reconstruction and tendon interposition - to determine pre- and postop HR QOL - Incidence of RLL at each f/up time point. Literature values from the same meta analysis ¹ will be used.
OUTCOME Measures	Patients will be assessed at preoperatively, and at 1, 3 and 5 years postoperatively. Outcomes as described by Li et al ¹ will be measured: grip strength, tip pinch strength, key pinch strength, pain, occurrence of adverse events, hand function.
Follow-up time	Patients will be part of a longitudinal follow-up program with follow-ups at 1, 3, 5 years.
Enrollment time	2 Years

STATISTICS

SAMPLE SIZE CALCULATION

Based on a publication from Davis et al² we expect the standard deviation in the study population for key pinch, tip pinch, and grip strength to be 0.82, 1.65 and 10.3, respectively. Setting alpha at 0.05 and beta at 0.10, and assuming a MIREDIF (Minimally Relevant Difference)of 0.5 x Standard Deviation, an attrition rate of 10%, and data to be approximately normally distributed, the required sample size will be 96 (\approx 100) subjects.

STATISTICAL PROTOCOL

Continuous variables (e.g. age) will be summarized using the mean and standard deviation (SD). If the distribution of measurements is asymmetrical, the median and the interquartile range will be provided. For ordinal and nominal data proportions should be employed. Inferential statistics will be based on the unpaired t-test, or the Mann-Whitney test, depending on normality of the data.

REFERENCES

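### The primary comparison with literature values has no allowance for between-study differences, so its 5% error and 90% power depend on conditions the plan does not state

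*Combined protocol and SAP*

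**What the plan says.** In the GENERAL INFORMATION table, the design row describes a "Non-controlled, prospective cohort study in single centre". The primary objective is to "compare functional outcome at 3 years after trapezio-metarcarpal arthroplasty with trapeziectomy and trapeziectomy with ligament reconstruction and tendon interposition". The comparator data are "Literature values obtained by a recently published meta analysis".

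SAMPLE SIZE CALCULATION expects SDs of 0.82 (key pinch), 1.65 (tip pinch) and 10.3 (grip), and sets the minimally relevant difference at half an SD. It continues: "Setting alpha at 0.05 and beta at 0.10", with "an attrition rate of 10%, and data to be approximately normally distributed, the required sample size will be 96", which is then rounded to 100. It gives no formula and does not say whether the test is one- or two-sided.

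STATISTICAL PROTOCOL names one approach: "Inferential statistics will be based on the unpaired t-test, or the Mann-Whitney test, depending on normality of the data".

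Neither section gives the number of literature patients, the number of literature studies, the precision of the literature means or any between-study variance.

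**The concern.** An unpaired t-test counts one source of uncertainty, the variation between patients within each group. When one group is a new single-centre cohort and the other is published results, there is a second source. Study means differ because of centre, case mix, measurement technique and timing. A single cohort without a concurrent control cannot separate those differences from the effect of the implant.

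If study means vary at all beyond sampling error, the planned test uses too small a standard error. Its intervals are then too narrow and its error rate exceeds the stated 5%. An ordinary difference between studies could be read as an effect of the prosthesis, and nothing in the planned output would warn the reader.

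The power has a second dependency. If the 96 is one arm of a two-arm calculation, the other arm has to come from the literature, and the plan does not say how large it is.

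**Working it through.** **Inputs from the plan.** Alpha 0.05, power 0.90, difference 0.5 SD, attrition 10%, stated size 96 (planned 100). The SDs cancel because the difference is set in SD units. **Assumed here, because the plan gives no values:** tau, the number of literature studies k, and the literature n (nL).

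**1. Reproducing the 96.** A two-sided two-sample t-test for 0.5 SD has power 0.8999 with 85 per group and 0.903 with 86 per group. So n = 86, and 86/0.9 = 95.6, which rounds up to 96.

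As a check on that inference, 24 variants were tried: one- or two-sided, one- or two-sample, t or z, and three attrition rules (rounded n/0.9, unrounded n/0.9, rounded n x 1.1).

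| Reading | Result after attrition |
|---|---|
| Two-sided two-sample t, 86/0.9 | 96 |
| Other five two-sided two-sample variants | 94-95 |
| One-sided two-sample | 76-78 |
| Two-sided, fixed literature value | 47-49 |
| One-sided, fixed literature value | 39-40 |

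Only the first gives 96. The figure is therefore consistent with one arm of an equal two-arm design.

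**2. Literature n needed for 90% power at tau = 0** (noncentral t).
- With 86 ARPE patients evaluable, power is 65%, 80%, 90% and 97% for nL = 30, 50, 86 and 200. The smallest nL giving 90% is 85; the normal approximation gives about 82.
- The planned 100 leaves 100 x 0.9 = 90 evaluable, and about 81 literature patients then suffice.

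**3. Effect of tau on the planned test.** In SD-squared units the test uses v = 1/nA + 1/nL, where nA is the number of evaluable ARPE patients. With study means varying by tau and k equally weighted literature studies, the true variance is V = v + tau^2(1 + 1/k). Then:

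Type I error = 2 x (1 - Phi(1.96 x sqrt(v/V)))

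For 86 v 86, v = 2/86 = 0.02326. With k = 4 and tau = 0.1, V = 0.02326 + 0.0125 = 0.03576, and 1.96 x sqrt(0.6504) = 1.581, giving 0.114.

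| tau (SD) | 0 | 0.05 | 0.1 | 0.2 | 0.3 |
|---|---|---|---|---|---|
| Type I error, planned test | 5.0% | 6.6% | 11% | 27% | 42% |
| SE allowing for tau (SD) | 0.152 | 0.162 | 0.189 | 0.271 | 0.368 |
| Power for 0.5 SD, allowing for known tau | 91% | 87% | 75% | 46% | 27% |

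A simulation with the t-test (200,000 runs) gave type I errors of 5.0%, 6.6%, 11.2%, 26.8% and 41.6%.

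Over k = 1 to 8 and nL = 30 to 200, type I error is 6-9% at tau 0.05, 8-19% at 0.1 and 17-42% at 0.2. A large literature sample does not cure this. With unlimited nL and tau^2 counted only once, tau = 0.1 still gives 15.1%.

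**4. Tipping value.** An observed 0.5 SD difference loses significance when tau exceeds sqrt(((0.5/1.96)^2 - v)/(1 + 1/k)) = sqrt((0.06508 - 0.02326)/1.25) = 0.183 SD. The range is 0.10 (nL 30, k = 1) to 0.21 (nL 200, k = 8). In the plan's units, 0.183 SD is 0.15 key pinch (x 0.82), 0.30 tip pinch (x 1.65) or 1.9 grip (x 10.3).

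**5. Example.** An observed key-pinch difference of 0.41 (0.5 x 0.82) has 95% interval 0.16 to 0.66 at tau 0, 0.11 to 0.71 at 0.1 and -0.02 to 0.84 at 0.2 (86 v 86, k = 4).

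**6. The 5% is per test.** Even at tau = 0, two comparisons on one outcome sharing the ARPE arm (86 in each group, correlation 0.5) give about a 9% chance of at least one false positive.

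**The case against.** Comparison with the literature is the declared design; the study calls itself non-controlled and claims neither superiority nor a causal effect. That stands, and it is why the point asks for no change of design or sample size.

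The size of the harm is unknown. The documents give no tau, k or literature n; a small tau does little damage; and the illustrative figures move with the model. Counting tau^2 once instead of with tau^2/k gives 10.1% and 23.5% at tau 0.1 and 0.2, in place of 11% and 27%. This also stands. What survives is the direction: any tau above zero puts the planned test's error above 5%.

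A reader might infer more in four ways, and the documents support none of them:
- *The 96 is wrong.* It reproduces exactly on a standard reading.
- *The false-positive rate is 27%.* That figure belongs to one assumed tau.
- *The study is underpowered.* If the literature holds well over 86 patients per comparator, power at tau = 0 exceeds 90%. The documents do not show the number either way.
- *86 literature patients is a stated assumption.* It is inferred from the reproduced calculation.

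Finally, a table over tau does not say which tau is true, so it cannot settle a borderline result. This is a real limit. The fix therefore also says how a significant test will be worded.

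**Conclusion.** The point holds as a conditional statement. Followed as written, the plan's only inferential method gives an error rate above 5% for the primary comparison whenever study means differ beyond sampling error. On the reading that reproduces the 96, the 90% power also needs about 81 to 86 literature patients per comparator. The plan states neither condition.

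The two-sided, two-sample reading is an inference from one matching figure, so confidence is medium. The magnitudes rest on assumed tau, k and literature n and are illustrations only. The plan should be changed, but the sample-size arithmetic is sound and the study remains feasible.

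**What to change.** **SAMPLE SIZE CALCULATION.** State that the 5% error is per test and assumes tau = 0. State that the 90% power assumes this as well, plus literature information comparable to the group size used in the calculation (apparently about 86 per comparator; the sponsor to confirm). Once the literature n has been extracted, restate the power for that n.

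**STATISTICAL PROTOCOL.** Keep the t-test as the planned test, run on summary mean, SD and n. Do not use Mann-Whitney where only summary literature values exist, because it needs individual values. If an outcome has no usable literature mean, SD and n, report it descriptively. Add:

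> Each ARPE-minus-literature difference in means will be reported with 95% intervals using variance s^2/n + SE(literature mean)^2 + tau^2 at tau = 0, 0.05, 0.1, 0.2 and 0.3 SD, where SE(literature mean)^2 contains tau^2/k at the same tau, and with the smallest tau at which the interval includes zero. A significant planned test will be described as a difference from the literature conditional on tau = 0, always together with that tipping value, and not as an effect of the prosthesis by itself.

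The tau^2/k term matters. If it is left out, type I error at tau = 0.2 is 6.9% with k = 4 and 12.5% with k = 1.

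Tabulating ARPE and literature pre-operative values side by side would help readers but is optional.

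**Cost.** No extra patients or visits. Some data must be extracted from the cited review and its studies. Intervals widen: power for 0.5 SD is about 87%, 75% and 46% at tau 0.05, 0.1 and 0.2 (86 v 86, k = 4). Some results will stay inconclusive.

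### The primary 3-year comparison with literature values gives the scheduled pre-operative strength and function values no stated role, so a baseline difference could pass for, or hide, a prosthesis effect

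*Combined protocol and SAP*

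**What the plan says.** The synopsis describes the design as "Non-controlled, prospective cohort study in single centre". Under PRIMARY Research objectives it states: "The primary objective is to compare functional outcome at 3 years after trapezio-metarcarpal arthroplasty with trapeziectomy and trapeziectomy with ligament reconstruction and tendon interposition". The comparator data are "Literature values obtained by a recently published meta analysis". There are thus two comparators, trapeziectomy alone and trapeziectomy with ligament reconstruction and tendon interposition, and neither is observed in the trial.

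Under OUTCOME Measures, the plan says "Patients will be assessed at preoperatively, and at 1, 3 and 5 years postoperatively". The outcomes listed there are grip strength, tip pinch, key pinch, pain, adverse events and hand function. Adverse events are outside this point.

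The STATISTICAL PROTOCOL provides descriptive summaries (mean and SD, or median and interquartile range if the distribution is skewed) and one sentence on inference: "Inferential statistics will be based on the unpaired t-test, or the Mann-Whitney test, depending on normality of the data". It mentions no change score, covariate, matching, or comparison of baselines with the literature patients. The one objective that names a pre-operative value is secondary and concerns a different outcome: "to determine pre- and postop HR QOL".

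**The concern.** Without a randomised or concurrent control, nothing in the documents makes the ARPE patients resemble the literature patients before surgery. Patients who start stronger tend to finish stronger, and a centre that measures higher before surgery is likely to measure higher afterwards too. An unpaired test on 3-year values cannot separate such a starting difference from an effect of the prosthesis. Recruiting more ARPE patients narrows the confidence interval but leaves the shift where it is.

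This is only one part of the general weakness of a literature comparison. It deserves its own point because the trial already schedules the data that could address it, at least in part.

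**Working it through.** **1. What the sample size implies about the tested variable.** Inputs from SAMPLE SIZE CALCULATION: alpha 0.05, beta 0.10, difference 0.5 SD, attrition 10%. A two-sided two-sample t-test needs 86 per group, and 86 / 0.9 = 95.6, rounded up to 96. The stated 96 therefore reproduces as one group of a two-sample comparison of means at a single time point, with no baseline term. That supports reading the tested variable as the 3-year value, but the text does not say so.

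**2. How much of a baseline gap carries over.** Let g be the gap in SD units. The share carried into the 3-year contrast depends on why the gap exists.

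- If patients with equal baselines have equal expected 3-year values in both sources, the shift is g × correlation × (3-year SD / pre-operative SD).
- If the gap is a stable offset, such as a different measuring device or a different sex mix, the whole gap carries over and the shift is g.

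**3. Illustration.** None of these inputs is in the documents: g = 0.2 SD, correlation 0.6, equal SDs, 90 ARPE patients (100 less 10%) and 86 literature patients (an assumed equal-size planning value, 96 less 10%).

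- Shift: 0.2 × 0.6 = 0.12 SD, up to 0.2 × 1 = 0.20 SD.
- As a share of the 0.5 SD minimally relevant difference: 0.12 / 0.5 = 24%, up to 0.20 / 0.5 = 40%.
- In the protocol's units (SDs 0.82, 1.65, 10.3): key pinch 0.10 to 0.16 (relevant difference 0.41), tip pinch 0.20 to 0.33 (0.825), grip 1.2 to 2.1 (5.15).

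Standard error = √(1/90 + 1/86) = 0.151 SD. The chance of false significance is P(|Z + shift/SE| > 1.96). Power for a true 0.5 SD difference that the gap opposes is P(Z < (0.5 − shift)/SE − 1.96).

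| Gap (SD) | Shift, carry-over 0.6 to 1 (SD) | False significance (nominal 5%) | Power (91% with no gap) |
|---|---|---|---|
| 0.1 | 0.06 to 0.10 | 6.8% to 10.2% | 83% to 76% |
| 0.2 | 0.12 to 0.20 | 12.5% to 26.4% | 71% to 51% |
| 0.3 | 0.18 to 0.30 | 22% to 51% | 56% to 26% |

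For a 0.2 SD gap, the assumed literature group size also matters. With 30 literature patients (SE 0.211) false significance is 8.8% to 15.8%. With the literature value treated as a fixed number (SE 0.105) it is 20.7% to 47.5%.

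**4. Which analysis removes the shift.** Simulation with the inputs of step 3 and no true effect:

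| Reason for the 0.2 SD gap | Unadjusted bias | Regression-adjusted bias | Change-score bias |
|---|---|---|---|
| Equal expected 3-year values at equal baseline | 0.12 | 0.00 | −0.08 |
| Stable offset | 0.20 | 0.08 | 0.00 |

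Each method is unbiased under one mechanism and biased under the other.

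**5. Tipping point.** For an observed 0.5 SD difference with 90 against 86 patients, the confidence limit reaches zero at a shift of 0.5 − 1.96 × 0.151 = 0.204 SD. The baseline gap needed is 0.204 / 0.6 = 0.34 SD at carry-over 0.6, and 0.20 SD at carry-over 1.

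**The case against.** The strongest reply is that the plan conceals nothing. It declares itself non-controlled, and baseline is only one of several differences from the literature. Adjusting for baseline alone may suggest a comparability that does not exist, and the planned summaries would describe the ARPE baseline anyway. Most of this stands, and it is why the conclusions need cautious wording. It does not answer the point. A summary of the ARPE cohort is not a comparison with the literature baseline, and disclosing a limitation is no reason to leave usable data unused.

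It is also fair that gap, correlation, SD ratio and literature group size are all assumed, and that a 0.1 SD gap does limited harm. The figures show the mechanism; they do not measure a problem in this trial. Whether the cited review publishes baseline or change values cannot be checked from the documents.

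Three stronger readings are tempting and unsupported.

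- A reader might infer that the 3-year result will be biased. The documents report no baseline data for either side, so no imbalance is shown. They also do not name the tested variable; if it is change from baseline, the bias takes a different form.
- A reader might infer that regression on baseline gives the correct answer, or that the carry-over is always gap × correlation. Both need equal expected 3-year values at equal baseline, and nothing in the documents establishes that.
- A reader might infer that the sample size is wrong. It reproduces and is not in question here.

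**Conclusion.** The point holds as an unquantified risk, on the natural reading that 3-year values are tested. The plan gives pre-operative strength and function no role in its primary comparison, so a baseline difference from the literature patients could be mistaken for a prosthesis effect or could conceal one. Under the stated assumptions (90 against 86 patients, equal SDs, correlation 0.6), a 0.2 SD gap would move the contrast by 0.12 to 0.20 SD. The lower figure assumes equal expected 3-year values at equal baseline; the upper assumes a stable offset. The change should be made, because it is cheap and uses data already scheduled. Confidence is medium, because the size of any real gap and the content of the published source are unknown.

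**What to change.** State in the SAP which variable is tested. Then, separately for each of the two comparators:

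1. Tabulate ARPE pre-operative values beside the published baseline values, where these are available.
2. Where published data allow, report two sensitivity analyses beside the unadjusted contrast: the change-from-baseline contrast, and the contrast regression-adjusted to the literature baseline mean. State the assumption behind each and present neither as definitive.
3. Otherwise, report a tipping-point analysis: the baseline gap that would bring the confidence limit to zero, with carry-over running from the regression slope observed in the ARPE cohort up to 1. Using the slope alone could overstate robustness.
4. Word all conclusions as a non-randomised comparison with residual confounding.

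The cost is SAP wording, extra literature extraction for two comparators and a small amount of analysis, with no new patient visit. There are two downsides. Item 2 depends on published values that cannot be checked here. Confounding by centre, era, surgeon and measurement remains whatever is done with baseline.

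### The Mann-Whitney branch of the only inferential rule cannot be run against published literature values, so a non-normal outcome has no usable pre-specified test for the primary objective

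*Combined protocol and SAP*

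**What the plan says.** The Design row of the General Information table describes a "Non-controlled, prospective cohort study in single centre". In the Primary Research objectives row, the 3-year functional outcome is to be compared with two other operations, trapeziectomy alone and trapeziectomy with ligament reconstruction and tendon interposition, using "Literature values obtained by a recently published meta analysis". The Secondary Research Objectives row repeats the comparison at 1 and 5 years with "Literature values from the same meta analysis". The outcomes are "grip strength, tip pinch strength, key pinch strength, pain, occurrence of adverse events, hand function".

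The Statistical protocol section has one sentence on inference: "Inferential statistics will be based on the unpaired t-test, or the Mann-Whitney test, depending on normality of the data". For asymmetrical data it adds only descriptive summaries, the median and interquartile range. The documents mention no individual comparator data, no reconstruction of such data, no one-sample test, no transformation and no other fallback.

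The sample-size paragraph assumes "an attrition rate of 10%, and data to be approximately normally distributed, the required sample size will be 96".

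**The concern.** An unpaired t-test can be computed from a mean, SD and n on each side, so published figures are enough for that branch. Mann-Whitney needs every individual value on both sides. Here one side is a set of published values, so the test that the plan prescribes for non-normal outcomes has no input for one of its two groups.

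The rank test has no other use in the plan. The quality-of-life objective ("to determine pre- and postop HR QOL") concerns the same patients before and after surgery, and the incidence of RLL is a proportion. Neither supplies two independent sets of individual measurements.

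The comparison with the literature is the primary objective. If a 3-year outcome is judged non-normal, the analyst must replace the prescribed test after seeing the data. The possible replacements do not answer the same question or have the same error rate, so the result could depend on an unplanned choice.

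**Working it through.** **1. The plan's own figure.** Inputs from Sample size calculation: alpha 0.05, beta 0.10, difference 0.5 SD, attrition 10%. Sidedness is not stated; two-sided is assumed. For an equal-n two-sample t-test the noncentrality is 0.5 × √(n/2) on 2n − 2 degrees of freedom.
- n = 85 per group: power 0.8999
- n = 86 per group: power 0.9032
- 86 / 0.90 = 95.6, rounded up to 96

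The stated 96 reproduces exactly, as the size of one group in a two-sample t-test. The three stated SDs cancel because the difference is expressed in SD units.

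**2. Do published summaries determine Mann-Whitney?** Illustration, with shape and shift assumed: a cohort of 90 built from gamma quantiles with skewness 1, and three comparators of 90 with the same mean and SD as each other. The cohort mean is 0.3 SD higher. The t statistic is 0.3 / √(2/90) = 2.01, the same in all three cases.

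| Comparator shape (same mean, SD, n) | t-test p | Mann-Whitney p |
|---|---|---|
| Same skewed shape | 0.046 | 0.034 |
| Normal | 0.046 | 0.13 |
| Mirror image | 0.046 | 0.35 |

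One set of published figures is compatible with three different Mann-Whitney results. The test therefore cannot be computed from those figures.

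**3. How often the branch would be reached.** The documents do not give this. Assuming Shapiro-Wilk at 5%, 90 evaluable patients (100 less 10%) and gamma-shaped data, the branch is triggered in about 37% of samples at skewness 0.5 and 93% at skewness 1.

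**4. Does the summary-value t-test hold its level?** Simulation with 90 patients on each side, both drawn from the same gamma shape, two-sided 0.05, 10,000 runs. Welch type I error at skewness 0, 0.5, 1, 1.5 and 2 is 5.1%, 4.9%, 4.9%, 4.7% and 4.8%.

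**5. What if the literature mean is treated as a known constant?** A one-sample t-test with n = 90 rejects when the difference exceeds 1.987 × SD/√90. If the literature mean itself comes from 90 patients, the true standard error of the difference is √2 times larger. The type I error is then about P(|Z| > 1.987/√2) = P(|Z| > 1.405) = 16%. Simulation gives 16% to 17% at every skewness from 0 to 2.

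**The case against.** **Frequency.** The 37% and 93% depend on a chosen normality test and a chosen skewness. The plan may intend graphical judgement, and the sample-size paragraph expects approximately normal strength data. This stands: the percentages are conditional and are not evidence about this trial.

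**The obvious fallback.** If Mann-Whitney cannot be run, the other test in the same sentence is the t-test, which behaves well. This limits the likely harm, but the fallback is not written down, and the written rule sends non-normal data elsewhere.

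**Inflated error.** A reader might infer that the plan carries a large type I error, because some improvised substitutes do: a signed-rank test against a fixed true literature mean rejects in 12% of null samples at skewness 1 and 35% at skewness 2. The documents do not support that reading, since the plan names no such test. For some substitutes, part of the excess comes from ignoring the literature's sampling error and not from skewness: signed-rank against a mean from 90 patients is already at 16% with zero skewness.

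**The illustration.** The 0.3 SD shift puts the t-test close to 0.05, and the mirror-image comparator is extreme. The table shows that the result is not determined by the published figures; it does not show how far apart results would be in practice.

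**Raw data.** If the sponsor means to obtain individual comparator data, the test could be run. Nothing in the documents says so, and the plan would need to state it.

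**Conclusion.** The concern holds as a feasibility fault in one branch. For comparisons with literature values, the test prescribed for non-normal outcomes cannot be computed, and nothing is specified in its place. This rests on one reading: that values from a published meta-analysis are aggregate summaries. It does not depend on any assumed skewness, normality test or comparator size. If every outcome is judged normal, no harm follows.

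Two stronger readings are tempting but unsupported. A reader might infer that the primary objective cannot be tested at all; the t-test branch can be run wherever the source gives a mean and a standard error, or an SD and n. A reader might also infer that the sample size is wrong or the study underpowered. The 96 reproduces. It implies a literature mean about as precise as one from 86 patients, but the documents give no literature standard error, so they do not show power below 90%.

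**What to change.** In the Statistical protocol section:

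1. Remove Mann-Whitney for comparisons with literature values. For continuous outcomes, specify a Welch-type t-test and 95% CI for the difference in means, computed from the cohort mean and SD and the published mean and its standard error, whatever the normality check shows. Keep median and interquartile range as description.
2. Where the source gives only a median, or no standard error can be derived, report the cohort estimate with its 95% CI beside the literature value as a benchmark, with no p-value and no claim of a difference between operations. A one-sample t-test should not fill this gap, given the 16% to 17% error shown above.

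Optional clarification in Sample size calculation: say that 96 is a per-group size that assumes a literature mean about as precise as one from 86 patients.

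The cost is one rewritten sentence and a few added lines; the sample size, visits and endpoints stay as they are. There are two downsides. Means are compared even when data are skewed, which can be less sensitive than a rank test on individual data would have been. Standard errors may also have to be extracted from the component studies, because the documents do not show what the cited review reports. The change covers continuous outcomes only; the inferential rule would still name no test for adverse-event proportions.

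### The plan's only inferential rule, for independent samples, does not fit a pre- versus postoperative HRQoL comparison in the same patients (minor, and only if that comparison is tested)

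*Combined protocol and SAP*

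**What the plan says.** The design is a "Non-controlled, prospective cohort study in single centre", so there is no second arm. On timing, the outcome row says "Patients will be assessed at preoperatively, and at 1, 3 and 5 years postoperatively".

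The secondary objectives include "to determine pre- and postop HR QOL". The same row closes by saying that "Literature values from the same meta analysis" will be used. It is unclear whether that covers HRQoL.

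Under the Statistical Protocol heading, the descriptive part provides means with SDs, medians with interquartile ranges for asymmetric data, and proportions for ordinal and nominal data. The inferential part is one sentence: "Inferential statistics will be based on the unpaired t-test, or the Mann-Whitney test, depending on normality of the data". It makes no exception for any endpoint. Neither a paired test, nor a change score, nor a repeated-measures model appears anywhere in the document.

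**The concern.** The unpaired t-test and the Mann-Whitney test treat the two sets of values as coming from different people. Pre- and postoperative HRQoL scores in this cohort do not. An analyst who tests the change by following the plan literally would discard the information that each patient serves as his or her own control.

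With positive within-patient correlation, the resulting test is conservative. The cost is lost precision: a modest HRQoL change could be reported as not shown when the data already collected would show it. A comparison of HRQoL with published values would be a different contrast, and this point takes no position on the test for that.

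**Working it through.** **The plan's own figure.** The sample size section assumes alpha 0.05, beta 0.10, a relevant difference "of 0.5 x Standard Deviation, an attrition rate of 10" per cent, and approximate normality. A two-sided, two-sample t-test at 0.5 SD and 90% power needs 85.03 per group, rounded up to 86. Then 86/0.9 = 95.6, rounded up to 96, which reproduces the stated figure. The calculation uses SDs for strength measures only; HRQoL plays no part in it.

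**Inputs for the HRQoL check.**
- Completers: 96 × 0.9 = 86.4, taken as n = 86 pairs (from the document).
- Within-patient correlation ρ = 0.3, 0.5, 0.7 (assumed; none is given).
- Equal SDs before and after, bivariate normal scores, changes in units of that SD (assumed).
- Change of 0.3 SD (assumed) and 0.5 SD (the protocol's relevant difference, set for strength, not HRQoL).

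**Standard errors.** The unpaired test uses √(2/n) = √(2/86) = 0.1525. The correct value is √(2(1−ρ)/n) = 0.1276, 0.1078 and 0.0835. The ratio is 1/√(1−ρ) = 1.20, 1.41 and 1.83.

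**Interval half-width, if the t-tests are turned into 95% intervals.** Unpaired: 1.974 × 0.1525 = 0.301 SD. Paired: 1.988 × SE = 0.254, 0.214 and 0.166 SD.

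**Size and power of the t-tests.** Paired power is from the noncentral t distribution; the unpaired size and power are simulated.

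| | ρ = 0.3 | ρ = 0.5 | ρ = 0.7 |
|---|---|---|---|
| True size of the nominal 5% unpaired test | 2.0% | 0.6% | 0.05% |
| Power at 0.3 SD, unpaired | 50% | 50% | 50% |
| Power at 0.3 SD, paired | 64% | 79% | 94% |
| Power at 0.5 SD, unpaired | 94% | 97% | 99% |
| Power at 0.5 SD, paired | 97% | 99.6% | >99.9% |

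From the unrounded values, the loss at 0.3 SD is 0.642 − 0.499 = 0.143, 0.785 − 0.498 = 0.287 and 0.944 − 0.499 = 0.445. At 0.5 SD it is 0.972 − 0.940 = 0.032, 0.996 − 0.966 = 0.030 and 1.000 − 0.990 = 0.010.

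**Rank test.** Mann-Whitney behaves the same way: simulated size 2.2%, 0.6% and 0.08%, and power at 0.3 SD about 47%.

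**Sensitivity.**
- With 90 completers (100 less 10%), power at 0.3 SD is 52 to 53% unpaired against 66%, 80% and 95% paired.
- At ρ = 0 the methods agree: about 50% power at 0.3 SD and 90% at 0.5 SD.
- At ρ = −0.2 the direction reverses, with a true size of about 7.4% (90 pairs).

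**Which paired method.** It is tempting to prescribe the signed-rank test for skewed changes. With 86 changes whose true mean is zero, the nominal 5% signed-rank test rejects about 12% of the time at skewness 1 and 34% at skewness 2. The paired t-test rejects about 5 to 6%. Under skewness the signed-rank test is not a test of the mean change.

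**The case against.** The strongest reply is that the plan never says it will test HRQoL. In the same row the functional objectives are to compare, whereas HRQoL is only to be determined, and the descriptive tools provided are enough for that. The title and primary objective concern comparison with published values, so the inferential sentence may have been written for that contrast alone. This stands, and it is why the point is conditional. A reader might infer that the plan commits to a wrong HRQoL analysis; the documents do not support that. What remains is that the rule is stated without limit, is the only one available, and would misfit if applied here.

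Second, the rule names tests and does not mention intervals, so the half-widths above extend it. That is fair; the standard-error, size and power results do not need the extension.

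Third, the size of the loss rests on assumed inputs. The documents give no HRQoL instrument, SD, correlation or relevant change. At 0.5 SD, the only relevant difference they state, the loss is slight. An unpaired test using all 96 preoperative and 86 later scores would also have a slightly smaller standard error: √(1/96 + 1/86) = 0.1485 against 0.1525, about 2.6% less. Both remarks are correct and keep the point minor.

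Fourth, a reader might infer a risk of false positives. For that the within-patient correlation would have to be negative, which is not the usual expectation and is nowhere suggested in the documents.

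**Conclusion.** The point holds as a minor, conditional one. The stated rule is for independent samples and does not suit a before-and-after contrast in the same patients. If that contrast is tested under the rule, the figures above apply, on the assumptions of equal SDs, 86 pairs and positive correlation of 0.3 to 0.7. The loss matters for modest changes and is nearly nil at 0.5 SD.

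It would be wrong to read this as a weakness of the 3-year primary comparison or of the stated 96: neither uses HRQoL. If HRQoL is only described, there is no error at all.

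**What to change.** Add to the statistical protocol one of two statements.

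- *If change is to be estimated:* change in HRQoL from the preoperative assessment to 1, 3 and 5 years will be reported as the mean within-patient change with a paired 95% confidence interval (paired t method; a bootstrap interval for the mean change if changes are markedly skewed), with the number of patients having both scores at each visit.
- *If not:* HRQoL will be reported descriptively only.

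In either case, state that the unpaired t-test and Mann-Whitney rule does not apply to within-patient comparisons. Do not switch to the signed-rank test because of skewness while reporting the mean change.

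The cost is two or three sentences, with no extra patients or visits. The outcome row does not list an HRQoL measure; the instrument has to be named before the wording can be final, since the method depends on the type of score.
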